6.5.3 Patient Reported Outcome Measures

The following outcomes will be collected at randomisation, and three monthly until patient is in remission. They will also be collected 1 month and 6 months post remission:

- Pain in the foot, ankle or leg measured, using the Numeric Pain Rating Scale.
- Health related quality of life assessed by the Medical Outcomes Short-Form Health Questionnaire (SF12)
- Psychological health status measured using the Hospital Anxiety and Depression Scale (HADS)
- EQ-5D-5L
- Economic Evaluation – Reported through a patient diary

6.5.4 Qualitative Study

The following will be explored in a patient interview with up to 14 participants which will take place one month after remission has been diagnosed.

- The participants' experience of being treated for CN measured
- The participants' views of the different interventions used in the study measured

6.6 Participant Timeline

	Active Phase (fortnightly visits throughout active phase of trial)										Remission	Follow Up after remission diagnosed			
Visit Number	1		6		11		18		25			FUV1	FUV2	FUV3	FUV4
month			3m		6m		9m		12m			1month	2months	3months	6months
Week **	0	2 weekly	W12	2 weekly	26	2 weekly	40	2 weekly	52						
Check In/exclusion criteria *	*														
Hand out FIS *	*														
Consent *	*														
Randomisation *	*														
Medical History *	*														
Foot Surgical history *	*														
Medication *	*	*	*	*	*	*	*	*	*	*	*	*	*	*	*
Record any amputation/s *	*	*	*	*	*	*	*	*	*	*	*	*	*	*	*
Record any infection/s *	*	*	*	*	*	*	*	*	*	*	*	*	*	*	*
Record any ulceration/s *	*	*	*	*	*	*	*	*	*	*	*	*	*	*	*
Record any falls *	*	*	*	*	*	*	*	*	*	*	*	*	*	*	*
Hand out patient diary *	*	*	*	*	*	*	*	*	*	*	*				
Collect & upload diary *		*	*	*	*	*	*	*	*	*	*				
Foot temperatures *	*	*	*	*	*	*	*	*	*	*	*	*	*	*	*
MRI (usual care) **	*									*					
MRI (Intervention arm) **	*		*		*		*		*						
Classification *	*														
Neuropathy Assess *	*														
Vascular Assess *	*														
BMI *	*		*		*		*		*		*				*
HbA1c (use existing if <3months) *	*														
Pain VAS *	*		*		*		*		*		*				*
HADS *	*		*		*		*		*		*				*
SF-12 *	*		*		*		*		*		*				*
EQ5D *	*		*		*		*		*		*				*
Study specific X-ray															*
		← Duration of active phase of treatment will be variable →													
Patient Interviews		← →													

6.7 Patient Assessments

Written informed consent to enter the trial must be obtained from participants after explanation of the aims, methods, benefits, and potential hazards of the trial and BEFORE any trial specific procedures are performed. The only procedures that may be performed in advance of written consent being obtained are those that would be performed on all patients in the same situation as standard care.

If the clinical team consider that a patient may be eligible, the patient information sheet should be handed to the patient and they should be given adequate time to consider if they wish to consent.

The tests and investigation as per the study protocol will be in addition to all the other treatment as standard, offered to patients with CN.

6.7.1 Randomisation Visit

These visits will take place in secondary care clinics.

Standard Care

- The off-loading device will be provided, if one has already been provided it will be removed and the foot/leg checked for any problems
- Assessment of neuropathy using the 10g monofilament and neurotheisometer

- Palpation of foot pulses
- Measurement of ABPI
- BMI recorded
- Measurement of HbA1c if not previously tested in the last 3 months
- Skin and nail care treatment given as necessary
- Treatment of any underlying wounds, ulceration and/or infection
- The off-loading device will be re-applied

Standard Care (Plus) – these tests and investigations are part of standard care but will be carried out according to trial WPDs. This will ensure standardisation across the site.

- X-ray of the affected foot
- MRI of the affected foot
- Foot temperature assessment

Study Specific Procedures

- The following questionnaires will be administered;
 - Health related quality of life assessed by the Medical Outcomes Short-Form Health Questionnaire (SF12)
 - Psychological health status measured using the Hospital Anxiety and Depression Scale (HADS)
 - EQ-5D-5L
- Participants will also be asked to complete a VAS to assess the pain they have experienced in their foot, ankle or leg over the last two weeks
- At each visit a patient diary will be issued and participants asked to complete it recording other visits to health care professionals. It will then be collected at the next visit and another one issued.

6.7.2 The “active phase” – up to 12 months

These visits will take place in the participant’s usual place of care (secondary care). Participants will attend for fortnightly visits. Standard care and study specific procedures will be carried out and recorded on the eCRF.

Study Specific Procedures

- The temperature assessment as per the WPD
- The participant diary will be collected and another issued for participants to complete over the next 2 weeks, until their next study visit.

In both arms remission will be defined as an absence of sub-chondral bone marrow oedema on MRI, as reported by a specialist musculoskeletal radiologist and/or the absence of clinical signs and symptoms of CN. The clinical team will interpret the results of the MRI report to determine remission. As per standard care at this point patients will have a foot and ankle X-ray.

Participants who develop bilateral CN during the study can continue in the trial. The trigger to arrange the MRI in the standard care arm will be based on the absence of signs and symptoms of active CN as assessed by the clinical team.

Patients randomised to A (Intervention – Serial MRI)

Patients randomised to the intervention group will have an MRI of their foot and ankle three monthly (at 3, 6, 9 and 12 months) until the CN has settled. Where possible the scan should be scheduled to coincide with study visits to minimise the number of additional hospital visits.

For participants in the intervention arm if the MRI report indicates to the clinical team that the CN is not in remission participants will continue in the active phase of the study, up to a maximum of 12 months.

Patients randomised to B (Standard Care)

Patients randomised to the standard care will undergo an MRI once the temperature difference between their feet is $\leq 2^{\circ}\text{C}$ on two separate occasions at least four weeks apart.

For participants in the standard care arm if the MRI report indicates to the clinical team that the CN is not in remission participants off-loading will be recommenced. Participants will continue in the follow up phase as per the trial protocol.

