5.1.1 Explanation for choice of comparators

Participants will be randomised to one of two arms;

(a) Serial use of MRI at 3, 6, 9 and 12 months to identify disease resolution and thus discontinuation of immobilisation plus standard care (**intervention**)

(b) Immobilisation discontinued on the basis of clinical remission determined by skin temperature measurement, which triggers an MRI (**standard care**)

The complications of the diabetic foot, osteomyelitis and CN, have well described appearances on MRI. The use of MRI in determining a diagnosis of CN in the early stages of disease when no signs are evident on plain radiology is well recognised⁴⁷. It has recently been suggested that the findings on MRI should be adopted as the criterion standard for establishing disease activity and remission in CN³⁸. This is because MRI has the greatest potential to allow monitoring the effect of treatment since it shows bone marrow oedema (inflammation). The majority of clinicians use the measurement of temperature described earlier, despite the increasing availability of MRI.

The literature suggests that MRI maybe superior to clinical techniques in determining the timing of termination of immobilisation. A small study demonstrated that mean healing time was significantly related to the baseline contrast medium uptake. A significant correlation between intensity of bone marrow oedema in MRI and clinical measures of soft tissue oedema and pain was found in another study⁴¹. A further small study suggested that semi quantitative scoring for bone marrow oedema and fracture on MRI might be useful in monitoring treatment of CN⁴².

There is a need for the use of MRI to be formally evaluated in a trial. This trial aims to explore the feasibility of using serial MRI in an attempt to reduce the duration of immobilisation of the foot.

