6.4.2 Arm B (Control – Standard Care and one additional MRI)

Immobilisation discontinued on the basis of clinical remission determined by skin temperature measurement and MRI. In the standard care arm participants will receive one additional MRI when the temperature measurements, X-ray and/or signs and symptoms indicate to the clinical team that the foot is in remission.

A temperature difference of $\leq 2^{\circ}\text{C}$ which is maintained or improves on two separate consecutive occasions for a period of ≥ 4 weeks will be the indicator to arrange the second MRI, to confirm the diagnosis of remission.

If participants in either arm of the trial have not reached remission at the end of the 12 month active phase of the study they will exit the study. Ongoing standard care will be provided by their clinical team.

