6.7.3 At three, six, nine and 12 months

In addition to standard care the following questionnaires will be administered to participants in both trial arms. Health related quality of life assessed by the SF-12, Psychological health status measured using the HADs and the EQ-5D-5L. Participants will also be asked to complete a VAS to assess the pain they have experienced in their foot, ankle or leg over the last 3 months. The three monthly assessments will only continue until the patient is in remission. Once the patient is in remission they will move to the follow up phase of the study.

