6.7.4 Follow up phase

In both arms once remission is confirmed by the MRI patients will then enter a rehabilitation/weaning phase. They will be transferred into a less restrictive off-loading device and then finally into footwear as per standard care. Participants will continue to attend for monthly trial visits for 3 months to monitor for any sign of relapse. The final visits will be at 6 months post remission. Standard care will continue to be provided.

At each visit study specific procedures will be carried out:

- The temperature will be assessed as per the WPD
- The participant diary will be collected and another issued for participants to complete until their next study visit. (This is only for the first three follow-up visits)

In addition to standard care and study specific procedures the participant will be asked to complete the following questionnaires and additional tests/investigations:

Follow Up - Month 1: VAS, SF-12, HADS and EQ-5D-5L will be completed.

Follow UP Month 6: VAS, SF-12, HADS and EQ-5D-5L completed. BMI will be recorded and an X-ray of the foot and/or ankle will be taken.

Relapse will be defined as a temperature difference of $>2^{\circ}\text{C}$ compared to the contralateral foot maintained for two or more occasions or further changes on imaging¹⁵. As per standard care the final decision as to whether the participant has relapsed will be at the discretion of the clinic team. If this occurs, then the participant will then recommence off-loading with a non-removable device. They will continue to be followed up as per the study protocol.

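### Section 6.7.2 keeps an Arm B participant whose MRI is judged not in remission in the follow-up phase, which conflicts with 6.4.2, 6.7.3 and 6.7.4 and leaves that participant's remission date contradictory

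*Protocol*

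**What the plan says.** In Arm B, a between-foot temperature difference of at most 2 °C, held over at least four weeks, triggers one additional MRI whose purpose is to confirm remission (6.4.2). If the clinical team reads that scan as negative for remission, 6.7.2 says: "not in remission participants off-loading will be recommenced. Participants will continue in the follow up phase as per the trial protocol". For an Arm A participant whose report is read the same way, the same section says that if the "CN is not in remission participants will continue in the active phase of the study, up to a maximum of 12 months".

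Entry to follow-up is described twice:
- 6.7.3: "Once the patient is in remission they will move to the follow up phase of the study".
- 6.7.4, headed Follow up phase: "In both arms once remission is confirmed by the MRI patients will then enter a rehabilitation/weaning phase".

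On the 12-month limit, 6.4.2 says that participants in either arm who "have not reached remission at the end of the 12 month active phase of the study they will exit the study".

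The protocol is not uniform on what ends immobilisation in Arm B. Section 5.1.1 has "Immobilisation discontinued on the basis of clinical remission determined by skin temperature measurement, which triggers an MRI", whereas 6.4.2 has "Immobilisation discontinued on the basis of clinical remission determined by skin temperature measurement and MRI". The 6.7.2 definition of remission, for both arms, is no sub-chondral marrow oedema on MRI, "as reported by a specialist musculoskeletal radiologist and/or the absence of clinical signs and symptoms of CN".

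**The concern.** A participant whose confirming scan did not confirm remission is placed in a phase that the neighbouring sections tie to remission. The phase a participant is in determines what the trial collects and when, so this is a pathway rule that the protocol itself has to settle.

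The remission date is the anchor for:
- the follow-up visits at 1, 2, 3 and 6 months (6.6, 6.7.4);
- the questionnaires 1 and 6 months after remission (6.5.3);
- the extra X-ray 6 months after remission (6.4);
- the count of participants needing further intervention within 6 months of remission (6.5.2);
- the exit at month 12 for those never in remission (6.4.2).

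Taken literally, 6.7.2 ends the fortnightly trial visits and three-monthly questionnaires while the team judges the disease active. Later data are then filed as post-remission. Two sites could reasonably apply different dates, and only in Arm B.

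**Working it through.** There is no figure in the plan to reproduce. The check sets the rules side by side and then counts what each one implies.

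**Step 1: apply each rule to one Arm B participant whose trigger MRI is judged not in remission.**
- 6.7.2: off-loading restarts and the participant is in follow-up.
- 6.7.3: not in remission, so not yet moved to follow-up.
- 6.7.4: MRI has not confirmed remission, so the entry condition is not met.
- 6.4.2: the confirming scan has failed. If this happens at month 12, the participant must leave the study, while 6.7.2 keeps the same person in follow-up.

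**Step 2: see whether another clause resolves it.** The relapse rule in 6.7.4 gives the same handling (restart off-loading, keep following up), but relapse needs a prior remission. The clinical alternative in the 6.7.2 definition could supply one at the temperature trigger. However, 6.7.2 also has the clinical team use the MRI report to determine remission, without distinguishing arms, and 6.7.4 asks for MRI confirmation in both arms. The restart wording implies that the device came off before the scan was read. That fits 5.1.1 but not 6.4.2.

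**Step 3: count the consequences.** The 6.6 timeline puts months 3, 6, 9 and 12 at weeks 12, 26, 40 and 52, with printed visit numbers 6, 11, 18 and 25. Arm B scans are not tied to these months, so the columns are illustrations.

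| Month of report (week) | 3 (12) | 6 (26) | 9 (40) | 12 (52) |
|---|---|---|---|---|
| Active phase: fortnightly visits left, (52 − week)/2 | 20 | 13 | 6 | 0 |
| Same, from printed numbers, 25 − visit number | 19 | 14 | 7 | 0 |
| Follow-up rule: scheduled trial visits (months 1, 2, 3, 6) | 4 | 4 | 4 | 4 |
| Active phase: three-monthly questionnaire sets left | 3 | 2 | 1 | 0 |
| Follow-up rule: sets labelled post-remission | 2 | 2 | 2 | 2 |
| Arm B last trial visit if the clock starts at the scan (report month + 6) | 9 | 12 | 15 | 18 |
| Arm A last trial visit if a later scan shows remission (that month + 6) | 12, 15 or 18 | 15 or 18 | 18 | none |
| Arm A exit month if never in remission | 12 | 12 | 12 | 12 |

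The active-phase counts are maxima, because they assume no remission before week 52. The two ways of counting differ by at most one visit. The gap between the rules is widest for early reports and reverses for late ones. These are trial visits; standard care continues in either phase.

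**The case against.** The strongest defence is that 6.7.2 is a deliberate Arm B rule. Sections 1.3, 5.1.1 and 6.11.5.1 all describe Arm B immobilisation as ending on temperature-defined clinical remission, and the 6.7.2 definition allows remission on clinical grounds. On that reading the participant is already in remission and in follow-up when the scan is read, the device has come off, and a discordant MRI is treated like a relapse. The difference from Arm A then follows from the design, since there the device stays on until the scan. The restart would be picked up by the further-intervention outcome in 6.5.2.

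This reading is coherent, and it explains why off-loading restarts rather than continues. It cannot stand together with 6.4.2, which stops immobilisation on temperature and MRI and makes the scan the confirmation, or with 6.7.4. If it is what the sponsor intends, those two sections are wrong. Some text has to change either way.

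Other parts of the defence stand. No section says in terms that follow-up opens only at MRI-confirmed remission: 6.7.3 mentions no MRI, and the 6.7.4 sentence names a rehabilitation/weaning phase, although under the Follow up phase heading. Section 6.4 allows extra visits on clinical need, so four is the scheduled number and not a cap.

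A reader might also infer that the arm difference biases the comparison of days with immobilisation, or that affected participants lose care. The documents support neither. They give no rate of temperature-MRI disagreement and no basis for a direction. Standard care continues throughout. Days in a restarted device are still days with immobilisation on the plain meaning. Event and censoring rules for the Cox model may properly sit in the SAP.

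**Conclusion.** The conflict is real and should be corrected. For Arm B participants whose trigger MRI is judged not in remission, 6.7.2 is inconsistent with 6.4.2, 6.7.3 and 6.7.4. Their remission date is therefore contradictory, along with every assessment that hangs on it. For one affected participant the difference ranges from 20 fortnightly visits (19 by the printed numbering) against 4 follow-up visits after a month-3 report, to 0 against 4 after a month-12 report. This assumes that the follow-up clock starts at the scan and that remission does not come before week 52.

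The number affected is unknown, within a planned 30 per arm. The trial is an unpowered feasibility study with exploratory between-group analyses, so no conclusion about efficacy is at risk. The finding still matters because estimates from this trial are meant to inform a definitive one. Temperature-guided against MRI-guided stopping is the intended contrast and is not criticised.

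**What to change.** In 6.7.2, replace the last sentence on Arm B so that participants judged not in remission return to, or stay in, the active phase up to a maximum of 12 months. Set their remission date when the clinical team later judges remission under the 6.7.2 definition, with no mandatory repeat MRI. Use that one date for the follow-up visits, the post-remission questionnaires, the X-ray, the further-intervention window and the month-12 exit.

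Align 5.1.1, 6.4.2 and 6.7.4 on whether the Arm B device comes off at the temperature trigger or after the MRI. Word 6.7.4 so that its MRI confirmation does not exclude this later clinical judgement.

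The cost is wording in four sections and some extra fortnightly trial visits for those affected. By the week count these are at most 20, 13 or 6 after a report at month 3, 6 or 9. Section 6.7.8 says that such patients are normally seen at least fortnightly during treatment, so the added burden should be small. Leaving out a compulsory second scan keeps Arm B at one additional MRI and preserves the contrast between the arms.

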6.7.3 At three, six, nine and 12 months

In addition to standard care the following questionnaires will be administered to participants in both trial arms. Health related quality of life assessed by the SF-12, Psychological health status measured using the HADs and the EQ-5D-5L. Participants will also be asked to complete a VAS to assess the pain they have experienced in their foot, ankle or leg over the last 3 months. The three monthly assessments will only continue until the patient is in remission. Once the patient is in remission they will move to the follow up phase of the study.

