6.11.4.2 Study Outcomes

Feasibility measures

- Number of eligible patients recruited, recruitment and retention levels, willingness of clinicians to participate in the study, and dropout rates.

Efficacy outcomes

- Days with immobilisation, for the intervention versus standard care will be measured
- Number of foot ulcers, infections, falls, minor and major amputations from randomisation to the end of the study
- Progression of foot deformity from randomisation – remission, and at the end of the study.
- Changes in psychological health status assessed by the Hospital Anxiety and Depression Scale (HADS) from baseline at, 3, 6, 9 and 12 months, remission and at the end of the study period.
- Changes in health related quality of life assessed by the Medical Outcomes Short-Form Health Questionnaire (SF12) from baseline at, 3, 6, 9 and 12 months, remission and at the end of the study period.
- Changes in reported pain experienced in the foot, ankle or leg as reported on a Visual Analogue Scale (VAS) from baseline at, 3, 6, 9 and 12 months, remission and at the end of the study period.

Economic Evaluation of resource use

- Collected through a patient diary

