6.12.3.1 Safety reporting

The intervention in the trial is increased frequency of MRI scanning which is compared with standard care of MRI scanning to confirm resolution of following temperature assessment of the affected limb. Contrast is not used for MRI scans in this study. Thus a pragmatic approach to safety reporting will be used. MRI scans are being performed in NHS trusts under routine clinical protocols. Adverse incidents resulting from MRI scans will be reported by the research site in line with the trusts clinical incident reporting policy. A copy of the incident form will be forwarded to the CI of the trial as soon as practicable. They will be forwarded to the Trial Sponsor on receipt by CI and will be reviewed by the TMG.

The following anticipated events are recorded as secondary outcomes. They will be reported as clinical events and reviewed by the TMG.

CN -RELATED SAFETY OUTCOMES

- Worsening of existing ulceration
- Infection of an ulcer
- Secondary ulceration on either limb
- Major and minor amputation
- Increase in pain

Off-loading – RELATED SAFETY OUTCOMES

- Falls as a consequence of wearing the off-loading device
- Iatrogenic skin irritation or lesions from off-loading device

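### Pain is recalled over two weeks at randomisation but over three months at 3, 6, 9 and 12 months, so the planned change from baseline mixes two recall periods

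*Protocol*

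**What the plan says.** Protocol 6.7.1 (randomisation visit) has participants complete a VAS "to assess the pain they have experienced in their foot, ankle or leg over the last two weeks".

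Protocol 6.7.3 (3, 6, 9 and 12 months, both arms, until remission) has them complete a VAS "to assess the pain they have experienced in their foot, ankle or leg over the last 3 months".

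Protocol 6.7.4 repeats the scale after remission without a recall period: "Follow Up - Month 1: VAS, SF-12, HADS and EQ-5D-5L will be completed" and "Follow UP Month 6: VAS, SF-12, HADS and EQ-5D-5L completed".

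Protocol 6.11.4.2 lists as an outcome the change in pain on a "Visual Analogue Scale (VAS) from baseline at, 3, 6, 9 and 12 months, remission and at the end of the study period".

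The scale has more than one name. Section 6.5.3 has "Pain in the foot, ankle or leg measured, using the Numeric Pain Rating Scale", section 6.4 describes a numerical VAS scored 0 to 10, and 6.7.1, 6.7.3, 6.7.4 and 6.11.4.2 say VAS. Sections 6.4 and 6.5.3 present one pain item for all time points and give no recall period. Nothing in the protocol explains the two windows or allows for the difference.

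**The concern.** A change score is interpretable when both of its ends measure the same quantity. Here the baseline end is pain in the fortnight before the visit, and the follow-up end is pain over a whole quarter. A quarter-long recall takes in pain from early in the interval, so it damps any steady change and does not describe pain at the visit.

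This matters even though the trial is a feasibility study. Section 6.5.1 lists statistical estimation for key outcome measures as a feasibility outcome, and 6.11.4.1 plans estimates of outcome variability to inform later sample sizes. The variance of a change score is Var(baseline) + Var(follow-up) − 2 × Cov(baseline, follow-up). The follow-up variance and the covariance both depend on the recall window. Values obtained with mismatched windows need not carry over to a definitive trial that uses one window. A statistical analysis plan cannot repair this, because two-week pain cannot be recovered from a three-month answer.

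**Working it through.** The protocol gives no figure for pain to reproduce: no mean, SD, trajectory or power calculation. The check compares the windows and then illustrates the consequence under stated assumptions.

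**Length of the windows.** Baseline: 2 weeks = 14 days (6.7.1). Three-monthly visits: 3 months, about 91 days or 13 weeks (6.7.3). Ratio: 91 / 14 = 6.5.

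**Overlap at month 3.** The timeline in 6.6 puts this visit at week 12, which is day 84. A 91-day recall reaches back 91 − 84 = 7 days before randomisation. It covers all the time since randomisation and 7 / 14 = one half of the baseline window.

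**Share of a fall that is recorded at month 3.** Assumptions, none taken from the protocol:
- a recalled score is the time average of pain over its window;
- the baseline score equals the starting level;
- for simplicity, month 3 is taken as week 13.

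Share recorded = 1 − (mean fraction of the fall still to come, averaged over the window).

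| Pattern of the fall | Two-week window | Three-month window |
|---|---|---|
| Linear over 13 weeks | 1 − 1/13 = 92% | 1 − 1/2 = 50% |
| Linear over the first 4 weeks, then flat | 100% | 1 − (4 × 1/2)/13 = 85% |
| Flat, then linear over the last 4 weeks | 1 − 1/4 = 75% | 1 − (9 + 4 × 1/2)/13 = 15% |

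Moving the visit to week 12, with a linear fall over those 12 weeks, changes little. The two-week window records 1 − 1/12 = 92%. The 13-week window holds one week at the starting level and 12 weeks averaging half the fall, so it records 1 − (1 + 12 × 1/2)/13 = 46%.

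**Later visits.** Section 6.6 puts them at weeks 26, 40 and 52. Thirteen-week windows there cover weeks 13–26, 27–40 and 39–52. If the fall is complete by week 13, these windows lie on the plateau and record essentially all of it. Under this pattern the distortion is a month-3 problem. A slower fall would carry it into later visits.

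**Between arms.** Section 6.7.3 gives the same item to both arms. With baseline measured identically under randomisation, the arm comparison at a given active-phase visit sets three-month recall against three-month recall.

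**The case against.** The strongest reply is that pain is one of many exploratory outcomes. The primary objective is feasibility (5.2), between-group analyses are exploratory, and days with immobilisation is the suggested primary efficacy outcome (6.11.4.1). Section 5.1 also describes the condition as often causing little pain, so the absolute error may be small. All of this stands and limits the weight of the point. It does not make the change score coherent.

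Several stronger readings are tempting, but the protocol does not support them:

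- **That the mismatch biases the comparison between arms.** One might argue that the immobilised share of each window depends on when remission was declared. But 6.7.3 stops the three-monthly assessments at remission, so those scored at these visits are still in the active phase, and both arms answer the same item.
- **That post-remission scores are contaminated by pain before remission.** If a three-month window were used one month after remission, two of its three months would precede remission. Section 6.7.4 states no window, so this is a gap to close and not a demonstrated error.
- **That the safety data are affected.** Section 6.12.3.1 lists "Increase in pain" among events to be reported clinically, but does not define it by the VAS.
- **That two different instruments are used.** The VAS is named at both randomisation and the three-monthly visits. What differs is the recall period. The varying names look like loose labelling of one 0-to-10 item and are a minor matter.

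**Conclusion.** The point holds as a contradiction within the protocol: 6.7.1 and 6.7.3 fix different recall periods, 6.7.4 fixes none, and 6.11.4.2 subtracts across them. What suffers is the meaning of the within-patient pain change, together with its SD and baseline correlation as planning values.

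That the windows differ by a factor of about 6.5, and that they overlap by about half the baseline window at month 3, follows from the text. The recorded shares of about 92% and 50% rest on time-average recall and a linear 13-week fall. The other two patterns shown give 100% against 85%, and 75% against 15%. No effect in scale points can be stated, because the protocol gives no pain levels. The point is modest in weight and does not threaten the feasibility conclusions.

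**What to change.** Name one pain scale and one recall window for every assessment: randomisation, 3, 6, 9 and 12 months, and 1 and 6 months after remission. The two-week window already used at baseline is one option; what matters is consistency. Align 6.4, 6.5.3, 6.7.1, 6.7.3, 6.7.4 and 6.11.4.2.

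For new assessments this changes the wording of one item and adds no visit or burden. Recruitment was planned from September 2017 and the amendment list runs to June 2020, so much of the data may already have been collected. A wording change during the trial would split the follow-up scores by window, and the analysis must flag this. For data already collected, record the window used at each assessment, report pain by visit with its window, and do not interpret raw change across windows as change on one scale. Any SD of change or baseline correlation passed to a definitive trial should carry the same label.
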